### **10.1. Institutional Review Board (IRB)**

The intent of the research program, the trial protocol, the patient information/informed consent form and any advertising material used to recruit subjects must be submitted to the clinical investigator's local IRB/IEC and its approval must be obtained prior to its use. A copy of the approval must be forwarded to Avid. When necessary, an extension or renewal of IRB/IEC approval must be obtained and also forwarded to Avid.

### **10.2. Informed Consent**

A signed, written informed consent must be obtained from each patient. A copy of the signed informed consent should be given to the patient for their records. A copy of the local IRB/IEC's approved version of the informed consent form must be forwarded to Avid or designee for review prior to being used to obtain patient consent.

### **10.3. Protocol Adherence**

The protocol must be read thoroughly and the instructions must be followed exactly. Where a deviation occurs, it must be documented, the sponsor/monitor informed, and a course of action agreed upon.

### **10.4. Documents Necessary for Initiation of the Study**

Avid must be provided with the following documents prior to the enrollment of any subjects:

- Original signed and dated Statement of Agreement page;
- Copy of the IRB/IEC and radiation safety committee approval (if applicable);
- Copy of the IRB/IEC stamped approved consent form;
- Name and location of the laboratory utilized for laboratory assays, and other facilities conducting tests, including laboratory certification number and date of certification if available. Avid may be responsible for supplying these to the investigator if a central laboratory is used;
- List of reference range laboratory values. Avid may be responsible for this if a central laboratory is used; and
- Any additional licenses required in order to order flortaucipir F 18.

### **10.5. Investigational Product Control**

The receipt of clinical supplies (i.e. starting material for flortaucipir F 18) must be documented at the site.

All drug supplies for this trial should be retained in a safe and secure place at all times during the trial. Flortaucipir F 18Injection should be prepared by a qualified PET manufacturing site and administered by a qualified individual under the investigator's supervision. An up-to-date drug inventory/dispensing record must be maintained. All drug supplies must be accounted for. After completion of the trial, all remaining clinical supplies must be returned to the sponsor or their representative.

## **10.6. Data Collection**

Electronic case report forms (eCRFs) will be used for this study. Individual patient files should include appropriate source documents, including but not limited to patient's medical records and laboratory test results. The files should include information such as visit dates, records of medical history, examinations administered, laboratory, concomitant treatment, any adverse event encountered and other notes as appropriate. These constitute "source data". All entries on the eCRFs must be backed up by source data. Original electronic versions of imaging studies are also considered source data and should be kept on file by the site/imaging center, and appropriate copies should be forwarded to Avid or a designated Imaging Core Lab as specified in the Imaging Manual.

Each patient's source file should include an original signed informed consent form. When the study is completed, the informed consent form should be kept on file with other study related records.

All original laboratory reports must be available for review in each patient's file. It is important that the original reports be available for review because of the possibility of inaccuracies or errors in transcribing data from original records to the eCRF.

The eCRFs must be kept in order and up-to-date so that they always reflect the latest observations on the subjects that are enrolled in the study. The eCRFs must be completed for each patient enrolled in the study and signed by the investigator. This should be done as soon as possible after completion of the patient's participation in the study. A monitor will verify the source data for all information on the eCRF.

## **10.7. Adverse Events**

All adverse events encountered during the clinical trial must be documented on the eCRF, whether or not considered drug-related.

Lilly must be notified immediately (as soon as possible, and in all cases within 24 hours) of a drug experience, condition, development, or event, which is considered serious. Lilly must be notified immediately of any findings with the use of the drug that may suggest significant hazards, contraindications, adverse drug reactions (ADRs) and precautions pertinent to the safety of the drug. The investigator will be requested to complete a separate report form in addition to the information on the CRF. See section 7.7.4 for reporting serious adverse events

If an SAE is determined to be unexpected (not previously reported or described by Avid), and study drug-related, Lilly will notify the investigator in writing. The investigator should forward this notification to the IRB/IEC within 24 hours of receipt.

## **10.8. Records Retention**

All correspondence (e.g., with Avid, IRB/IEC, etc.) relating to this study should be kept in appropriate file folders. Records of subjects, source documents, and drug inventory sheets pertaining to the study must be kept on file. Records must be retained until the date a marketing application (NDA) is approved for the drug for the indication for which it is being investigated, or until 3 years following the date of clinical study termination or completion, whichever is later. If no application is to be filed or if the application is not approved for such indication, records should be kept until 3 years following the date of clinical study termination or completion.

If an investigator moves, withdraws from an investigation, or retires, the responsibility for maintaining the records may be transferred to another person who will accept the responsibility. Notice of transfer must be made to and agreed upon by Avid.

## 11.2. Study Flow Chart

Evaluations/Procedures	Screening Visit a	Flortaucipir F 18 Imaging Visit	End of Flortaucipir F 18 Imaging (prior to discharge)	Follow-up Phone Call
Signed Consent	X			
Demographics	X			
Medical History/Neurologic Disease History	X			
Concomitant Meds	X	X		
Vital Signs b	X			
ECG	X			
MMSE	X			
Serum beta-hCG c	X			
Urine Pregnancy Test d		X		
flortaucipir F 18 scan		X		
Evaluation by a physician e	X	X	X	
Adverse Events	X	X	X	X
Serious Adverse Events	X	X	X	X

- Screening may take place over several days. All assessments must be performed within 30 days of the F-AV-1451 imaging session.
- Vital signs (pulse, respiratory rate, supine blood pressure). Weight will be taken at the imaging visit.
- Serum beta-hCG pregnancy test at screening for females of childbearing potential.
- For women of childbearing potential, a negative urine pregnancy test must be obtained within 24 hours prior to the flortaucipir F 18 injection.
- A physician or physician designee

1 LIST OF ABBREVIATIONS AND DEFINITIONS OF TERMS

Table 1: Abbreviations and Definitions of Terms

Aβ	amyloid-β
AD	Alzheimer’s disease
AE	adverse event
ATC	Anatomical therapeutic chemical classification
BMI	body mass index
CIP	Clinical investigational plan
cm	centimeters
CRO	contract research organization
DBP	diastolic blood pressure
ECG	electrocardiogram
eCRF	electronic case report form
IND	investigational new drug
IV	Intravenous
K _d	dissociation constant
kg	Kilograms
max	Maximum
MBq	Megabecquerel
mCi	Millicuries
MCI	mild cognitive impairment
MedDRA	Medical Dictionary for Regulatory Activities
min	Minimum
MMSE	Mini-Mental State Examination
mSv	Millisievert
MUBADA	Multiblock barycentric discriminant analysis
n	number of subjects
nM	Nanomolar
PET	positron emission tomography
SAE	Serious adverse event
SBP	systolic blood pressure
SD	standard deviation
SOC	system organ class
SOP	standard operating procedure
SUV _r	standardized uptake value ratio
TEAE	treatment-emergent adverse event
WHO	World Health Organization

2 INTRODUCTION

Flortaucipir F 18 (¹⁸F-AV-1451) (originally named [F-18]T807 by Siemens Molecular Imaging Biomarker Research group) is a positron emitting radiopharmaceutical developed for in vivo imaging of tau protein aggregates (Xia et al., 2013). Image assessment showed tracer deposition on brain PET scans to be consistent with that expected for a tracer of aggregated tau protein. Flortaucipir (¹⁸F) initially entered the brain and was subsequently eliminated from the brain in clinically normal and amyloid negative cognitively impaired subjects, yielding only a diffuse pattern of background activity, whereas a regionally distinct gray matter distribution of increased tracer retention was observed in amyloid positive cognitively impaired subjects (Pontecorvo et al., 2017). Preliminary analyses of our Phase II longitudinal study (A05, exploratory cohort) also indicate a relationship between the level and pattern of flortaucipir uptake at baseline, and the rate of decline on cognitive tests over an 18-month period (Mintun, AAIC 2017). These results suggest that it may be possible to use flortaucipir PET scans to enrich clinical studies for subjects with a desired level of AD pathology and a more homogeneous rate of cognitive decline, thus increasing power to detect a treatment effect. Specifically, Lilly and Avid desire to conduct treatment trials at the earliest stage of AD neuropathology to maximize potential patient benefit.

I5T-MC-AACG is a proposed anti-amyloid trial that intends to target subjects with a certain distribution and density of tau neurofibrillary tangles that are hypothesized to be appropriate for such a trial. It is thought that patients with no tau will progress so slowly that a clinical treatment effect could not be discerned, and those with a large tau burden may not be responsive to anti-amyloid therapy as their cognitive impairment is driven primarily by tau pathology. The overarching goal of AV-1451-A23 is to test this hypothesis by pre-screening subjects with flortaucipir F 18 who have been diagnosed with suspected Alzheimer's disease and have indicated their interest to consider participation in trials such as the AACG Lilly therapeutic clinical trial.

3 STUDY OBJECTIVES

The primary objective is to pre-screen subjects via a flortaucipir scan, who have objectively verified cognitive impairment and etiology diagnosed or suspected to be due to Alzheimer's disease, and have indicated their interest in participating in Lilly sponsored trials that require tau imaging for inclusion such as AACG.

The secondary objective of the study is to expand the flortaucipir F 18 safety database.

4 STUDY DESIGN

4.1 General Design

Study ¹⁸F-AV-1451-A23 is a multicenter screening study in subjects with early symptomatic AD (where early symptomatic AD refers to the combination of 2 stages: prodromal AD [MCI-AD] and mild AD dementia).

All subjects will provide informed consent before starting any study procedures. This prescreening study targets subjects who are interested in participating in AD therapeutic clinical trials and have expressed a preliminary interest in a trial like the AACG trial, and who are not known to have met any of the exclusion criteria for trials like AACG based on medical history and clinical examination. However, consent for this protocol does not constitute consent for the AACG trial or any other trials, and subjects who qualify for this protocol may still fail to qualify for trials like AACG or other trials based on the results of this protocol or based on additional testing performed in those subsequent trials.

Screening assessments may take place over several days and will be performed within 30 days prior to flortaucipir F 18 injection. Screening assessments will include demographic information, cognitive testing, disease history, concomitant medications, vital signs, ECG and medical history. Subjects who are deemed eligible to continue will complete a flortaucipir PET scan.

A physician or a licensed/credentialed medical professional (i.e., a PET technologist, imaging center nurse or a regional equivalent) designated by the site principal investigator must assess or evaluate the subject prior to administration of flortaucipir F 18 injection to determine if they are still suitable to undergo the scan.

All subjects will receive a single IV bolus administration target dose of 370 MBq (10 mCi) of flortaucipir F 18 injection followed by saline flush. At approximately 75 minutes following injection, a continuous 30-minute brain scan will be performed.

The injection site will be observed for excessive inflammation or damage to the surrounding tissue at the injection site. Adverse events will be continuously monitored during the flortaucipir PET imaging visit. Subjects who experience an adverse event will not be discharged from the imaging center until the event has resolved or stabilized. A follow-up phone call to the subject, or informant where applicable, will be conducted within 2 or 3 business days of the imaging day, but not before 48 hours post-injection, to confirm subject well-being and to collect any new adverse events.

A physician or a licensed/credentialed medical professional (i.e., a PET technologist, imaging center nurse or a regional equivalent) designated by the site principal investigator must assess or evaluate the subject prior to discharge from the imaging center to evaluate the subject's readiness for discharge.

Subjects who meet eligibility criteria will participate in this protocol until they complete their flortaucipir PET scan, or they discontinue, withdraw consent, or if the sponsor decides to end this protocol early.

4.2 Discussion of Study Design

This trial is designed to pre-screen subjects via a flortaucipir scan, who have objectively verified cognitive impairment and etiology diagnosed or suspected to be Alzheimer's disease, and have indicated their interest in participating in Lilly sponsored trials that require tau imaging for inclusion, such as AACG.

4.3 Method of Assignment of Subjects to Treatment Groups

Flortaucipir F 18:

All subjects will receive a single IV bolus administration target dose of 370 MBq (10 mCi) of flortaucipir F 18 Injection.

4.4 Blinding

A blinded design is not used for this trial, because all subjects will receive the same medication.

4.5 Determination of Sample Size

This is a pre-screening study that targets subjects who are interested in participating in AD therapeutic clinical trials and have expressed a preliminary interest in a trial like the AACG trial. Therefore, approximately 500 subjects will be enrolled in this study.

5 CHANGES IN THE CONDUCT OF THE STUDY OR PLANNED ANALYSES

5.1 Changes in the Conduct of the Study

There were no changes in the conduct of the study at the time of preparing this statistical analysis plan.

5.2 Changes from the Analyses Planned in the Protocol/CIP

There were no changes in the analyses planned in the Protocol/CIP at the time of preparing this statistical analysis plan.

6 BASELINE, EFFICACY AND SAFETY EVALUATIONS

6.1 Schedule of Evaluations

Evaluations/Procedures	Screening Visit ^a	Flortaucipir F 18 Imaging Visit	End of Flortaucipir F 18 Imaging (prior to discharge)	Follow-up Phone Call
Signed Consent	X			
Demographics	X			
Medical History/Neurologic Disease History	X			
Concomitant Meds	X	X		
Vital Signs ^b	X			
ECG	X			
MMSE	X			
Serum beta-hCG ^c	X			
Urine Pregnancy Test ^d		X		
flortaucipir F 18 scan		X		
Evaluation by a physician ^e	X	X	X	
Adverse Events	X	X	X	X
Serious Adverse Events	X	X	X	X

- a. Screening may take place over several days. All assessments must be performed within 30 days of the ¹⁸F-AV-1451 imaging session.
- b. Vital signs (pulse, respiratory rate, supine blood pressure). Weight will be taken at the imaging visit.
- c. Serum beta-hCG pregnancy test at screening for females of childbearing potential.
- d. For women of childbearing potential, a negative urine pregnancy test must be obtained within 24 hours prior to the flortaucipir F 18 injection.
- e. A physician or physician designee

6.2 Time Point Algorithms

6.2.1 Relative Day

The date of first dose of study drug (flortaucipir F 18) will be considered relative day 1, and the day before the first dose of study drug will be relative day -1. Relative days will be calculated as follows only when the full assessment date is known (i.e., partial dates will have missing relative days):

For days on or after the first dose of study drug:

Date of Assessment – Date of First Dose of Study Drug + 1.

For days before the first dose of study drug:

Date of Assessment – Date of First Dose of Study Drug.

6.2.2 Windows

No window algorithm is being used for this study.

6.3 Screening Assessments

Screening may take place over several days. All screening assessments will be performed within 30 days prior to flortaucipir F 18 injection. Screening assessments will include:

- Informed consent for subject;
- Demographics (age, gender, years of education, race, ethnicity); weight;
- Medical history, concomitant medications;
- Vital Signs (pulse, respiration rate, supine blood pressure)
- A resting 12 lead ECG will be performed to assess the subject's cardiac status. If an ECG was performed within the last 12 months of the flortaucipir (¹⁸F) PET Imaging Visit and is available for review, the ECG does not need to be repeated.
- ApoE status, if available;
- Disease history (date/months since symptom onset, date/months since diagnosis, family history of relevant neurologic disease);
- Cognitive status interview, including MMSE;
- A physician will see the subject during the screening visit.
- For women of childbearing potential, a negative serum pregnancy test must be obtained at the screening visit

Weight will be displayed in kilograms (kg), height will be displayed in centimeters (cm). Weights and heights recorded in alternate units will be converted to the units being

displayed using standard conversion formulas. Body mass index (BMI) will be calculated as weight (kg) divided by height squared (cm²).

APOE4 Positive is any subject with at least one of their two APOE alleles as an E4 allele.

Each subject's age (years) will be calculated based on his/her date of informed consent and will be truncated to a whole number. Because only year of birth is collected, January 1 will be imputed for the month and day of birth. Age will be calculated as the number of months between the date of informed consent and the imputed birthdate, divided by 12. Age will be rounded to the nearest integer.

The MMSE (Folstein et al., 1975) is a brief instrument used to assess cognitive function in elderly subjects. The instrument is divided into 2 sections. The first section measures orientation, memory, and attention. The maximum score for the first section is 21. The second section tests the ability of the subject to name objects, follow verbal and written commands, write a sentence, and copy figures. The maximum score for the second section is 9. The range for the total MMSE score is 0 to 30, the sum of each correct answer, with higher scores indicating better cognition.

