#### 7.1.1. Screening Visit:

Screening may take place over several days. All screening assessments will be performed within 30 days prior to flortaucipir F 18 injection.

Screening assessments will include:

- Informed consent for patient;
- Demographics (age, gender, years of education, race, ethnicity); weight;
- Medical history, concomitant medications;
- Vital Signs (pulse, respiration rate, supine blood pressure)
- An ECG will be performed to assess the participant's cardiac status. If an ECG was performed within the last 12 months of the flortaucipir (F) PET Imaging Visit and is available for review, the ECG does not need to be repeated. ApoE status, if available;
- Disease history (date/months since symptom onset, date/months since diagnosis, family history of relevant neurologic disease);
- Cognitive status interview, including MMSE;
- A physician will see the patient during the screening visit.
- For women of childbearing potential, a negative serum pregnancy test must be obtained at the screening visit

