7.8 Examination of Subgroups

No subgroup analysis will be performed.

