8.4 Demographic and Other Baseline Characteristics

All baseline summaries will be based on the safety population.

Frequency distributions and summary statistics for demographic and baseline variables will be presented across all subjects. Key demographic and baseline characteristics to be summarized include: age, gender, race, ethnicity, height, weight, BMI, highest level of education, alcohol history, recreational drug use history, smoking history, MMSE, and ApoE Genetic testing.

All demographic and baseline characteristics data will be presented in listings.

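### SAP 6.3 divides weight in kg by height in cm squared, so BMI programmed as written comes out 10,000 times smaller than in kg/m²

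*SAP*

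**What the plan says.** SAP section 6.3 (Screening Assessments) sets the display units first: "Weight will be displayed in kilograms (kg), height will be displayed in centimeters (cm"). Measurements taken in other units are to be converted into those two. The next sentence is the derivation: "Body mass index (BMI) will be calculated as weight (kg) divided by height squared (cm²").

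BMI appears in two other places in the SAP. The abbreviation list in section 1 expands it as "body mass index" and gives no unit. Section 8.4 includes it among the key baseline variables to be summarized ("age, gender, race, ethnicity, height, weight, BMI" and others) and adds: "All demographic and baseline characteristics data will be presented in listings". The protocol does not mention BMI, so section 6.3 is the only rule a programmer has.

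**The concern.** BMI is conventionally weight in kilograms divided by the square of height in metres. The SAP squares height in centimetres and applies no scaling factor. This cannot be read as loose notation for a calculation done in metres, because the preceding text has just put height in centimetres and the unit conversions it mentions lead to kilograms and centimetres only.

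The sentence is an operative derivation rule that feeds a planned table and listing. If it is programmed as written, every BMI statistic is wrong by a constant factor. If the programmer corrects it without comment, the output no longer matches the written specification. Both outcomes are avoidable.

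**Working it through.** **Inputs from the documents.** Weight in kg, height in cm, and the formula weight divided by height squared in cm² (SAP 6.3). The documents state no BMI value or unit, so there is no figure of the plan's own to reproduce. The reference unit, kg/m², is the standard convention and is not taken from the documents.

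**Ratio of the two definitions.**

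- Literal rule: BMI_lit = W / H², with W in kg and H in cm.
- Conventional rule: BMI = W / (H/100)² = 10,000 × W / H².
- Ratio: BMI / BMI_lit = 100² = 10,000, whatever W and H are.

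**Illustration.** The documents give no heights or weights, so these subjects are assumed, chosen to span a plausible range.

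| Weight (kg) | Height (cm) | Literal rule (kg/cm²) | Conventional (kg/m²) | Literal value at 3 decimals |
|---|---|---|---|---|
| 45 | 150 | 45/150² = 0.002000 | 45/1.50² = 20.00 | 0.002 |
| 60 | 160 | 60/160² = 0.002344 | 60/1.60² = 23.44 | 0.002 |
| 75 | 170 | 75/170² = 0.002595 | 75/1.70² = 25.95 | 0.003 |
| 90 | 180 | 90/180² = 0.002778 | 90/1.80² = 27.78 | 0.003 |
| 110 | 185 | 110/185² = 0.003214 | 110/1.85² = 32.14 | 0.003 |

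**Effect on the printed table.** At two decimals a literal value first prints as 0.01 when it reaches 0.005, which corresponds to 0.005 × 10,000 = 50 kg/m². Every assumed subject above would therefore print as 0.00. The mean, SD, median, quartiles and range planned in SAP 7.1 all scale by the same constant, so at ordinary precision the BMI row would carry almost no information.

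**Where BMI is used.** It is absent from the eligibility criteria (Protocol 5.3), the imaging analyses (SAP 8.10) and the safety analyses (SAP 8.11). SAP 7.8 states: "No subgroup analysis will be performed". SAP 7.2 says that covariate adjustment does not apply to the primary analyses, and the planned analyses are descriptive throughout. The error is confined to one row of the baseline table and its listing.

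**A separate query on height.** BMI needs height, but the screening list in Protocol 7.1.1 ("Demographics (age, gender, years of education, race, ethnicity); weight") does not name it, and neither does the list in SAP 6.3. The schedule footnote on vital signs, in SAP 6.1 and Protocol 11.2, covers only weight: "Weight will be taken at the imaging visit". SAP 6.3 does refer to recorded heights. The eCRF is not among the documents, so whether height is collected cannot be settled here. The unit error does not depend on the answer.

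**The case against.** The best case on the other side is that this is close to editorial. Values of 0.002 to 0.003 look wrong at first sight, and SAP section 9 places all displays under the analysis vendor's quality-control procedures, so a false table is unlikely to survive to the report. Most programmers would use kg/m² without being told. The documents do not contradict a BMI figure of their own, because they give none, and the reference unit comes from convention. Nothing in the study turns on BMI.

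All of that stands, but it bears on the consequence and leaves the rule itself wrong. Quality control checks output against the specification, and here the specification is at fault. The reliance on convention is real but uncontroversial.

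The height query is also fairly open to challenge. SAP 8.4 lists alcohol, smoking and recreational drug history, which the visit lists do not name either, so absence from those lists does not show that height goes uncollected. It should be read as a request for confirmation only.

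**Conclusion.** The concern holds. The BMI rule in SAP 6.3, taken literally, gives values too small by a factor of exactly 10,000 relative to kg/m². The factor rests only on there being 100 cm in a metre and on kg/m² being the intended unit; the assumed body sizes serve as illustration. The practical weight is low: one descriptive baseline variable is affected, by a known constant, and correct values can be recovered from the height and weight reported with it. It is an optional but worthwhile correction.

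**What to change.** Replace the BMI sentence in SAP 6.3 with: BMI (kg/m²) = weight (kg) / [height (cm) / 100]². Label the BMI row and listing column in kg/m². The cost is one SAP sentence, with no new data where height is already recorded and no change to design or analysis.

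Separately, confirm that the eCRF collects height. If it does, name it in the screening list or in the schedule footnote that already covers weight. This is a further small edit, and it would touch the protocol as well if the two schedules are to stay identical.

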### **5.3. Selection of Subjects**

#### **5.3.1. Inclusion Criteria**

Patients must meet the following criteria to enroll in this study:

1. Men or women, at least 60 to 85 years of age at the time of consent;
2. Patients with gradual and progressive change in memory function for  $\geq 6$  months;
3. Patients who have a Mini Mental State Examination (MMSE) score between 20-27 inclusive;
4. Patients who are willing to undergo a PET scan using flortaucipir F 18;
5. Patients who give informed consent or have a legally authorized representative (LAR) to consent for enrollment; and

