8.3 Protocol Deviations/Violations

Subjects who entered the study even though they did not satisfy one or more of the inclusion/exclusion criteria will be listed. Deviations/violations from the protocol will be documented, the Avid/contract research organization (CRO) monitor will then be informed and a course of action will be agreed upon.

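### Imputing January 1 for every birthdate makes derived age overstate completed age at consent, by 0.5 year on average with truncation and 1.0 year with rounding.

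*SAP*

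**What the plan says.** SAP 6.3 defines age at informed consent. The birthdate is completed by rule: "Because only year of birth is collected, January 1 will be imputed for the month and day of birth". The formula follows: "Age will be calculated as the number of months between the date of informed consent and the imputed birthdate, divided by 12". The section gives two rules for reaching a whole number. Age "will be truncated to a whole number", and two sentences later "Age will be rounded to the nearest integer".

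Age is reported in the baseline table under SAP 8.4: "Key demographic and baseline characteristics to be summarized include: age, gender, race" and further variables. SAP 7.1 gives continuous variables a mean, SD, median, quartiles, minimum and maximum.

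The entry criterion in Protocol 5.3.1 is "Men or women, at least 60 to 85 years of age at the time of consent". For departures from entry criteria, SAP 8.3 says: "Subjects who entered the study even though they did not satisfy one or more of the inclusion/exclusion criteria will be listed". It does not name the data source for the age check. Protocol 7.1.1 and SAP 6.3 both list age among the screening demographics.

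**The concern.** When only the year of birth is known, any fixed day is a guess. January 1 is the one guess that cannot be too late: it always gives the longest possible interval to consent. The errors therefore do not cancel over subjects, and every wrong age is wrong in the same direction.

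At stake is the accuracy of the age summary, and in particular its maximum. A maximum of 86 or 87 in a trial with an upper age limit of 85 looks like an entry violation even when every subject was compliant. Choosing between truncation and rounding changes the size of the bias but does not remove it.

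**Working it through.** The documents state no computed figure on this point, so there is none to reproduce. The check applies the SAP's own algorithm.

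**Inputs**
- Imputed birthdate: January 1 of birth year B (SAP 6.3).
- Age = months from imputed birthdate to consent, divided by 12, then truncated or rounded (SAP 6.3).
- Entry range: 60 to 85 at consent (Protocol 5.3.1), with 85 read as completed years, that is, up to the 86th birthday.
- Assumption: birthdays and consent dates are independent and spread evenly over the year.

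**Set-up.** Let Y be the consent year and D = Y − B. Let f be the fraction of the year elapsed at consent and b the birthday as a fraction of the year.
- True completed age = D if b ≤ f, and D − 1 if b > f.
- Derived age before conversion = D + f with January 1, and D + f − 0.5 with July 1.

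Four cells cover all subjects. Their probabilities come from integrating f, or 1 − f, over each half-year:
- f < 0.5 and b ≤ f: 0.125
- f < 0.5 and b > f: 0.375
- f ≥ 0.5 and b ≤ f: 0.375
- f ≥ 0.5 and b > f: 0.125

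**January 1, truncated.** Derived age is D. The error is +1 whenever b > f: 0.375 + 0.125 = 0.50. Mean error +0.5 year.

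**January 1, rounded.** Derived age is D in the first half of the year and D + 1 in the second. The errors over the four cells are 0, +1, +1 and +2. Overstated: 1 − 0.125 = 87.5%. Mean: 0.75 × 1 + 0.125 × 2 = +1.0 year.

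**July 1, truncated.** Derived age is D − 1 in the first half and D in the second. The errors are −1, 0, 0 and +1. So 12.5% are low and 12.5% high, with mean 0.

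**July 1, rounded.** Derived age is D throughout, the same as January 1 truncated: 50% high, mean +0.5 year.

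| Imputed day | Conversion | One or more years high | One year low | Mean error (years) |
|---|---|---|---|---|
| January 1 | truncate | 50% | 0% | +0.5 |
| January 1 | round | 87.5% | 0% | +1.0 |
| July 1 | truncate | 12.5% | 12.5% | 0 |
| July 1 | round | 50% | 0% | +0.5 |

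Enumerating every birthday against every consent date in one calendar year, with whole months, gave the same picture: 49.8% high with mean 0.498 for January 1 truncated, and 87.6% high with mean 1.003 for January 1 rounded. Counting fractional months (days/30.4375) moves these shares by less than 0.5 percentage point. It allows one negligible understatement, for a January 1 birth with a January 1 consent.

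**At the limits.** The shares at a single true age match the overall ones. Of true 85-year-olds, about 50% appear as 86 under truncation. Under rounding about 75% appear as 86 and 12.5% as 87. Of true 59-year-olds, about 50% appear as 60 under truncation and about 87.5% as 60 or 61 under rounding.

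**Examples** (illustrative dates)
- Born 15 October 1932, consent 15 March 2018: true age 85, derived 86.17, shown as 86 under either rule.
- Born 15 October 1958, same consent date: true age 59, derived 60.17, shown as 60 under either rule.
- Born 15 February 1933, same consent date: true age 85, derived 85.17, correctly shown as 85 under either rule.

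**The case against.** The strongest objection is that little depends on this variable. The study is a single-group descriptive pre-screen with no covariate adjustment (SAP 7.2) and no subgroups (SAP 7.8), and the SAP discloses the rule and its reason. SAP 8.6 uses the same January convention for onset and diagnosis dates with month and day missing. This stands as a limit on importance: no imaging or safety result changes.

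A second objection is about the target. Against exact decimal age, D + f − b, the January 1 truncated age is unbiased on average, because f and b both average 0.5. That is correct. The bias is measured against completed years, which is what truncation to a whole number aims at and the natural reading of the entry limits. The individual errors at the limits remain on either view.

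A third is that July 1 is not clean either. With truncation, about 12.5% of true 60-year-olds would appear as 59, an error January 1 does not make under whole-month counting, and about 12.5% of true 85-year-olds would still appear as 86. This also stands. Birth year alone cannot classify age at 60 or 85 under any imputation.

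A reader might go further and infer that the plan misjudges eligibility: compliant 85-year-olds listed as violators, 59-year-olds passed as eligible, or subjects dropped from the safety population, which SAP 8.1.2 limits to those eligible. The documents do not support that. No section ties derived age to eligibility, to the SAP 8.3 listing or to the analysis populations, and sites may judge age from source records. Those effects would follow only if derived age were used for the check.

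**Conclusion.** The derived age overstates completed age at consent by rule: by 0.5 year on average in 50% of subjects with truncation, or by 1.0 year on average with 87.5% overstated under rounding. The mean, median and range in the SAP 8.4 table are biased upward, and a compliant 85-year-old whose birthday falls after consent is shown as 86. The sizes assume evenly spread birthdays and consent dates. The statement about age 85 also assumes that 85 means completed years; the overstatement itself does not.

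The effect on checking the age criterion is conditional on a use of derived age that the documents do not state. SAP 4.5 says "approximately 500 subjects will be enrolled in this study", but without an age distribution the number of them affected at either limit cannot be computed. This is a minor point that is cheap to correct.

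**What to change.** 1. In SAP 6.3, impute July 1 in place of January 1, keep truncation, and delete the sentence that rounds to the nearest integer. The two parts belong together: July 1 with rounding still overstates by 0.5 year on average.
2. In SAP 8.3, state that compliance with inclusion criterion 1 comes from the site's recorded eligibility decision, or from recorded age at consent if it is entered, and not from derived age.

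The cost is a few words of SAP text and a line of code, with no new data. Reported mean age falls by about 0.5 year if the program would have truncated and about 1.0 year if it would have rounded. Some true 60-year-olds will display as 59 and some true 85-year-olds as 86. A table footnote saying that age is derived from year of birth would keep these from being read as entry violations.
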